The event distant metastasis can be detected radiographically as PSMA PET/CT is recommended at suspicion of relapse. Biopsy is also accepted and MRI, CT, bone scintigraphy, NAF-PET, ultrasound or clinical examination may also be accepted with further confirmation, e.g. biopsy or laboratory tests. If the event “distant metastasis” is based on tests without biopsy or PSMA positivity the event shall be confirmed at MDT.

Biochemical relapse

Phoenix criteria are used for definition of the event biochemical relapse, defined as a PSA increase of 2 ug/l from nadir. The date of recurrence is the first date with a PSA level of nadir + 2. The PSA level must be confirmed by a second PSA measurement performed at minimum two weeks later.

Local recurrence

The event local recurrence is defined as a local PSMA positive lesion. Local recurrence after definitive radiotherapy should be confirmed by biopsy from the site of suspected recurrence if the result has implication for the treatment. MRI, CT, ultrasound or clinical examination may also be accepted with further confirmation, e.g. biopsy.

Regional relapse

The event regional recurrence is defined as at least one regional PSMA positive lesion. Biopsy is also accepted and MRI, CT, ultrasound or clinical examination may also be accepted with further confirmation, e.g. biopsy or laboratory tests. If the event “distant metastasis” is based on tests without biopsy or PSMA positivity the event shall be confirmed at MDT.

Death

Cause and time of death is collected from electronic patient charts for up to 20 years. If no information is available, data will be retrieved from the national death register.

Endpoints related to toxicity

Self-reported quality of life (QoL)

QoL is registered as described in the paragraph “Follow-up and Data Collection” using EORTC QLQ-PR25 and QLQ-C30.

CTCA registered toxicity

Toxicity is registered using CTCAE v 5.0 as described in the paragraph “Follow-up and Data Collection”

Radiotherapy Quality Assurance (QA)

[figure not shown]
The radiotherapy (RT) approach in this study is a highly advanced treatment combining several modalities. Tumour targets are identified by multi-parametric MRI, PET and CT. The individualised dose-plans are optimised for tumour dose while minimising doses to healthy critical tissue. The treatment is delivered by linear accelerators using daily on-line imaging and treatment adaptation.

A comprehensive quality assurance (QA) program is essential to ensure reliability and reproducibility in RT trials in general. This is especially the case in multi-center trials with different local routines and equipment. Past trials have shown significant variability in various parts of the treatment planning process, underscoring the need for QA, as seen in the CHHiP and PEACE V-STORM trials (77,78). The QA program needs to cover all aspects of the treatment chain: imaging, delineation, treatment planning, treatment delivery, and dosimetry.

The study aims to develop and standardise procedures across centres by utilising modern imaging data, collected with strict protocols. The data will be used to create a strategy compatible with routine RT practices. Workshops regarding treatment planning and plan quality will be conducted using established national imaging and planning archives (DcmCollab). The consensus plans will serve as a benchmark for the plan complexity that the treatment delivery machines must be able to reproduce. This in turn will form the basis of the QA-program across participating institutions described in detail in Appendix A.

Timeline

Figure: Gantt chart

Organisation

The study is led by the core group consisting of oncologists and medical physicists based in three regions of Denmark. A trial management group and a data management group will also be established.

Core Group

The core group consists of [name], [name], [name], [name], [name], [name] and [name]. The group has substantial experience in prostate cancer research on an international level. The core group is responsible for the scientific content of the trial, funding of the trial and establishing the infrastructure of the trial. The core group has regular online and onsite meetings.

Sponsor

The sponsor is the head of the department of Oncology, Rigshospitalet, [name]. A letter of support is enclosed in the appendices section.

Trial Management Group

The Trial Management Group (TMG) includes investigators from all participating centres and the members of the core group. The TMG will be responsible for the day-to-day running and management of the trial and will meet regularly by teleconference or at meetings.

Data Monitoring Committee

The group will be led by [name]. The group will secure the completeness of the data, quality of data, monitor the progression of the trial and make the data available for the IDMC.

Independent data monitoring

An independent data monitoring committee (IDMC) will also be established. The Independent Data Monitoring Committee (IDMC) is the only group who sees the confidential, accumulating data from the trial. Reports to the IDMC will be produced by the Data Monitoring Committee.

Work Packages

To manage the study's technical issues during planning and running the trial, we have defined the following work packages:

- Imaging: leaders [name] and [name]
- Radiotherapy dose planning: leader [name]
- Radiation treatment delivery: leader [name]
- Patient data and toxicity registration: leader [name]

We have agreements from physicians and physicists to establish the listed work packages. The groups represent the Danish centres broadly.

The aim of a work package is overall to ensure the highest possible level of reproducibility and quality in real-world settings across the participating institutions within the different project tasks.

Patient involvement

The trial has been presented to two patient representatives with a history of PCa; [name] and [name]. Both representatives have reviewed and provided insightful feedback on the project, and have also consented to being mentioned in funding applications. Both found the scientific questions asked in the trial of high relevance for PCa patients. Patient engagement and collaboration within the trial management group remain ongoing.

Ethical consideration

The trial will follow the current Helsinki Declaration (2013). The trial can only start when approved by the Ethical Committee.

The trial consists of one standard arm and three arms with experimental therapy. At every participating centre, there is an investigator, responsible for the trial, who assures that every patient is informed, orally and in writing, about the trial with respect to the content of the trial and the detailed follow up before the patient can enter the trial. This includes benefits and risks from participating in the trial. All patients receive a trial specific patient information booklet, which follows the Danish guidelines for patient information.

Potential benefits for the patient

The potential advantages for a patient participating in the trial is to have fewer fractions in the experimental arms (12 fractions versus the standard arm of 20 fractions), and to reduce the risk of distant metastases by increasing the dose to the intraprostatic tumor lesion.

Potential risks for the patient

The potential disadvantage for the patient is an increased risk of late side effects from the lower urinary tract and rectum and bowel.

The side effects and risks of curatively intended combined LHRH-treatment, and radiotherapy for prostate cancer is well described and the patients will be informed about the risks before treatment.

We cannot exclude an increased risk of urinary and/or genito-urinary toxicity in the short treatment arm as the primary endpoint is non-inferiority for increased toxicity. A careful collection of recorded toxicity is therefore an important part of the study. An independent data monitoring committee will oversee the data during the study (see paragraph on independent data monitoring committee).

The concept of the study is to test if increased dose to intra prostatic lesions without increased dose to the surrounding organs improves tumour control. For the patients in the boost arm, we will also ensure that dose to urethra is kept the same dose level as the non-boost arm. However, we cannot completely exclude a higher risk of urinary toxicity.

Withdrawal of consent

The participant can withdraw from the trial at any time, and he does not have to give a reason for withdrawal. If he chooses to have standard therapy, this will be external beam radiotherapy according to the current DAPROCA guidelines.

Patients, who for some reason do not receive the allocated therapy, are to be treated at the doctor's discretion. The analysis of data will be according to the intention-to-treat principle. Unless the patient

does not accept it, he is followed as all other patients in the trial regarding the primary and secondary endpoints.

For patients not receiving the allocated therapy or withdrawing from the trial at a later point of time, the date of exit from the trial is registered as also the reason if possible. The patient is informed about the burden of follow up before randomization to minimize withdrawal from the trial. The patient can withdraw from the trial without telling a reason at any time.

Possible benefits for society

If successful, the societal impact of the trial will be significant, resulting in improved treatment outcomes at a lower cost. The current diagnosis-related cost for a fraction of radiotherapy (DRG takst) is set at 2,709 DKK. Reducing the number of fractions from the current standard of 39 to 12 is projected to decrease the annual DRG cost of radiotherapy by approximately 25 million DKK (approximately 3.4 million EUR), assuming 350 patients per year. However, the actual reduction may be slightly less due to the increased complexity of the fractions.

Additionally, there is potential for savings in subsequent salvage therapy if the disease control is superior. A health economics task is outlined in the Gantt chart in section “Timeline”. A comprehensive procedure list can be extracted from the Danish registries on the randomised patients to facilitate a high-quality assessment of health economics. An external partner with domain knowledge will be involved once the data is mature for this analysis.

The healthcare sector is globally responsible for 5% of greenhouse gas emissions (79,80). Chuter et al. found that 226.9 kg of CO₂ equivalents were emitted during a 20-fraction RT course for a patient with prostate cancer (81). More than 80% of these CO₂ emissions were related to transportation. Therefore, the environmental impact of RT will also be substantially reduced if the trial successfully decreases the number of fractions from the current standard of 39 to the emerging standard of 20, and further down to 12 fractions in the experimental arm.

Economic issues

This trial protocol is initiated and developed by the DAPROCA10 Core Group, and the trial will be nationwide in Denmark. Radiation therapy is standard to all patients included in this trial, so there will be no additional costs regarding the radiation therapy for the participating departments. The reduction of the number of treatments may reduce the costs for the participating centers.

The individual radiation therapy department participating in the trial will cover the costs related to follow up. The principal investigator and the trial responsible staff have no economic interests in the trial.

Further funding will be applied for to cover the study procedures. The project has received 2 million DKK from Danish Cancer Foundation (KB) which has no influence on the planning and conduct of the

study or the interpretation of results. Additional funding will be applied for, and the ethics committee will be informed if such funding is achieved. The participant information document will be updated accordingly.

The participants will not have extra costs and no compensation will be given to participants.

Funding

[name] has a 3-month grant from Rigshospitalet to develop the focal boost technique up to the grant start date. Furthermore, we have funding for 1 year research assistant time for [name], to facilitate the imaging study and data analysis of the studies preparing for this national trial.

A grant of 2,000,000 DKK from the Danish Cancer Society has been secured for preparing the randomised national trial, implementing imaging, and training physicians in defining intraprostatic targets to optimise radiotherapy planning and treatment.

A grant of 200.000 DKK from DCCC has recently been given to the group for supporting the completion of the trial protocol, grant application and meeting activities.

Insurance

The participants in the study are covered by the Patient Compensation Association.

Publication

The results from this trial will be published irrespective of them being positive, negative, or inconclusive. After approval by the Ethical Committee, the trial will be registered at www.clinicaltrials.gov. Co-authorship follows the Vancouver guidelines.

The Trial Management Group (TMG) will form the basis of the Writing Committee and will advise on the nature of all publications. The TMG will decide on authorship and co-authorships, however, for the paper on primary end points, co-authorship will likely be assigned to the one representative from each center with >5% of the accrued patients and two co-authors from centres recruiting 30% or more of eligible patients in the trial. Investigators who contribute to designing, collection, validation and analysis or in other ways contribute significantly to the trial may also earn authorship.

Any publication, that is not pre-planned, on the primary and secondary endpoints cannot be accepted until the primary and secondary endpoints from the entire study have been published. Other information from the trial (e.g. local quality assurance on radiation therapy or of the morbidity evaluations) can be published with approval from TMG.

Projects defined at a later point of time using results/data from this trial, can be conducted and published with approval from TMG.

All publications from this trial must be on behalf of the DAPROCA10 TMG and either "DAPROCA10" must be in the title or stated "on behalf of the DAPROCA10 TMG". Relevant funding e.g. DCCC and the Danish Cancer Society must be mentioned and acknowledged when results are published (contact the principal investigator or the DAPROCA for more details).

Appendices

Addition of focal boost to primary radiotherapy for prostate cancer in 12 or 20 fractions: A large DAPROCA randomised trial.

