The DAPROCA multidisciplinary group is planning a large trial to answer two pertinent questions of how to improve radiotherapy for high - and intermediate risk prostate cancer:

1. Will increasing dose to intra-prostatic cancer lesions improve outcomes with respect to prostate cancer without increasing toxicity?
2. Is it possible to shorten the treatment without increased toxicity?

The success of both increased dose to intra-prostatic cancer lesions and shortening of treatment, which means treatment with fewer treatment fractions with higher dose per fraction, is most likely dependent on high quality, high precision radiotherapy (RT) planning and delivery. A French randomised trial in prostate cancer demonstrated improved rectal toxicity scores ($p=<0.03$) and biochemical control with image guidance, and the MIRAGE randomised trial demonstrated improvements with smaller margins and more precise delivery (1-3). Many European clinics, including the Danish RT-clinics are able to provide high quality RT to all patients as per national consensus guidelines and in this study, we aim to further develop and implement this high quality opportunities in order to deliver hypofractionated RT and to boost the dose to intraprostatic lesions in all participating centers.

Background

Prostate cancer (PCa) is the second most common malignancy in men worldwide (4), and the most common cancer in Denmark (5). The incidence of PCa has been increasing in most countries and varies between countries. In Denmark, the incidence is now 124/100.000 men per year (5), and the median age for men diagnosed with PCa is 72 years (6). In the public, PCa is considered to have a good prognosis, but the fact is that the mortality is high with 1323 Danish men annually dying from PCa, exceeding the age-standardised breast cancer mortality ([nordcan,https://nordcan.iarc.fr/en](https://nordcan.iarc.fr/en)). The prognosis and the treatment of PCa depends on patient factors, as well as the histology grade, the prostate specific antigen (PSA) level, and the extent of disease (7).

This trial focuses on the group of patients with intermediate and high risk PCa, who have a risk of relapse of 25 - 60% (8,9) and a risk of getting metastatic disease of up to 20 % after 5 - 8 years (10-12).

Large, randomised trials have shown improved oncological outcomes, including overall survival, and disease specific survival for RT combined with androgen deprivation therapy (ADT) compared to ADT

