A strategy to improve outcome is dose escalation to the cancer lesions in the prostate. The FLAME randomised trial (NCT01168479) demonstrated improved biochemical control, reduced local failure (LF) and reduced regional + distant metastatic failure (8,28). Toxicity is the limiting factor, and the boost dose was strictly limited depending on organ at risk exposure (OAR) in the FLAME trial. A dose response analysis for biochemical control indicated that patients with higher achieved boost doses experienced better tumour control (29). At the same time, the data suggested reduced toxicity as a result of further consideration of radiation dose to OARs and improved urethral sparing in particular (30). The question is therefore whether the addition of a focal boost can be established as standard of care.

A study larger than FLAME is needed in order to confirm effectiveness with freedom from distant metastases (FFDM) as an improved primary endpoint, compared to biochemical control which was used as primary endpoint in FLAME. However, while endpoints based on biochemical relapse free

survival are not surrogate for overall survival in localised prostate cancer, FFDM is now shown to be a valid surrogate endpoint for OS in trials of localised prostate cancer (31-33). Biochemical control is used as a secondary endpoint in the current study to confirm the FLAME results and study heterogeneity of treatment effects as detailed in the statistics section.

Shortening of treatment duration

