Based on the randomised trials showing benefit of radiotherapy with combined hormone- and radiotherapy compared to hormone therapy only (9,13,14), 3 months pre-irradiation castration is standard for high-risk patients in many institutions (7). Studies have addressed weakening MRI signals and PSMA PET-uptake after castration (60,61). However, there is not enough data to guide us to the optimal imaging to define intra-prostatic lesions in patients who are treated with a combination

of medical castration and radiotherapy. Currently this topic is being investigated in a phase 2 study (Danish Ethical Committee 2303938), conducted by the research group to prepare for the present study.

Additional improvements in delivery, such as MRI based image guidance, improved CT based image guidance, or adaption of the daily dose plan to the anatomy of the day etc. may improve outcomes further (58,62). If participating centers implement follow local adaptive strategies for adaptation due to anatomical changes, the center must document the procedures.

Study design

Statistical considerations

The reference schedule is 20 fractions, 5 fractions per week, without boost. For this reference schedule we assume the following outcomes of relevance to the statistical sample size calculation:

- 5-year biochemical control: 87%
- 5-year freedom from distant metastasis: 90% with sensitivity analysis 85%-90% 5 year OS: 82%.
- Prevalence of grade 2 or worse gastrointestinal(GI) toxicity: 10% at ~1 year
- Prevalence of grade 2 or worse genitourinary(GU) events: 20% at ~1 year

Dropout is assumed to be dominated by death from other causes. The expected OS of 82% yields a dropout rate of $\eta=0.039$ when assessing endpoints where death is a competing event (Such as freedom from distant metastasis). We account for this dropout in the calculations below.

Table showing overall design

		Fractionation trial Trial tests for non-inferiority of short fractionation	
		12 fractions	20 fractions
Boost trial Trial tests for superiority of focal boost	Boost	Boost: 60 Gy/12 fractions (EQD2=110 Gy) Prostate: 50 Gy/12 fractions (EQD2=80 Gy) Pelvic: 37 Gy/12 fractions (EQD2=48 Gy)	Boost: 75 Gy/20 fractions (EQD2=110 Gy) Prostate: 60 Gy/20 fractions (EQD2=77 Gy) Pelvic: 45 Gy/20 fractions (EQD2=48 Gy)
	No boost	Prostate: 50 Gy/12 fractions (EQD2=80 Gy) Pelvic: 37 Gy/12 fractions (EQD2=48 Gy)	Prostate: 60 Gy/20 fractions (EQD2=77 Gy) Pelvic: 45 Gy/20 fractions (EQD2=48 Gy)

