Primary endpoints and dimensioning

Superiority trial: Effect of focal boost

Primary endpoint will be freedom from distant metastasis (FFDM), which is concluded to be a strong surrogate of OS in localised PCa (32). The reference level for FFDM is a challenging parameter to address as it should be expected to improve with recent advances in the adjuvant systemic treatments. However, the population of this study is the highest risk RT patients, and we should therefore expect a distant metastasis (DM) rate that is on average higher than in other trial populations. The FLAME trial reported a DM rate of approximately 11% at 78 Gy dose to the primary target (Data supplement in FLAME). The current trial has a higher risk profile in patient uptake. We thus assume a 10% DM rate (90% FFDM) as a conservative reference level at 5 years, but with sensitivity analysis down to 85% FFDM. Furthermore, a single sided alpha of 5% is used to assess the alternative hypothesis that the boost arms have a FFDM rate at five years of 95% or better. We will assume 5 years uniform accrual plus 1-year additional follow-up (32). This primary sample size assessment yields the need for 254 patients in each of the four arms for a total of 1,016 patients to reach a power of 80% for the one-sided test for superiority on FFDM. The power after an additional 4 years of follow-up under the same assumptions increases to 96%.

Sensitivity analyses for the less conservative power calculations assume 85% FFDM and yield a power of 91% after 5+1 years and 99% after 5+5 years with the same number of patients and relative risk.

Non-inferiority of short fractionation

Defining boundaries of non-inferiority at 15% for GI events and 27% of GU events we have >80% power to detect inferiority with 1,016 patients on both endpoints.

Conclusion

In conclusion, 4x254 patients is a realistic sample size from a recruitment perspective. It is also sufficient to have an impact on guidelines for future patients if the trial is successful.

Secondary endpoints with formal power assessment

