This is a safety metric and a planned publication is made comparing all four arms with approximately 100 patients each.

Late GI and GU toxicity dose-response

A pre-planned dose response analysis is made after 600 patients accrued. 3D dose matrices and organ segmentations will be exported, and the dose converted to equivalent dose in 2 Gy fractions (EQD2) to avoid bias from the trial arm. This part of the analysis can be fully automated (67) and the trial arm will not be disclosed to the investigators. Subsequently, a dose-response relationship can be derived for rectum, bladder, urethra and bowel (68). A Novo Nordic funded data science infrastructure, DESIRE, can be used to collect the relevant data from the referring institutions and computationally time-dose-fractionation considerations. The open source model TotalSegmentator, which is being made available in the DESIRE infrastructure and for individual institutions, may greatly improve our ability to perform the dose response-analyses without relying on time-consuming human annotations (69-71).

Heterogeneity of treatment effect

Pre-planned heterogeneity of treatment effect will be performed on both the fractionation trial and the boost trial for the below mentioned covariables and outcomes. Heterogeneity of treatment effect will be assessed using appropriate statistical methods, such as interaction terms in the regression modelling.

With regards to superiority of focal boost we will test for heterogeneity for age effect of HR for FFDM and test for age and treatment modality for HR of biochemical control.

With regards to non-inferiority of short fractionation, we will test for age effect on HR for GI and GU toxicity and test for treatment modality effect on HR for GI and GU toxicity.

Further details of these pre-planned tests will be designed in the cancer society funded phase of the trial in the first half of 2025. A statistical analysis plan will be published prior to initiating data analysis.

Risks and contingency plans

A pre-planned trial assessment after 3 years with an expectation of 600 patients is planned (see section “Timeline”). Here, the data monitoring committee and the trial steering group will assess both the feasibility and progress of the trial in relation to the accrual plan and statistical sample size. In addition the assessment will involve scouting the recent literature and active trials and discuss possible needs for adjustments based on emerging evidence.

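### Does the boost question need a pre-set toxicity limit because the Purpose asks for benefit without added toxicity?

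*Protocol*

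**What the plan says.** The first of the two questions in the Protocol's Purpose section reads "Will increasing dose to intra-prostatic cancer lesions improve outcomes with respect to prostate cancer without increasing toxicity". The background section on increased dose to intra-prostatic lesions adds "The question is therefore whether the addition of a focal boost can be established as standard of care".

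The formal design is narrower:

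- **Design table (Study design).** The boost factor is labelled "Trial tests for superiority of focal boost". The fractionation factor is labelled as a non-inferiority trial.
- **Superiority trial: Effect of focal boost.** The endpoint is FFDM: "a single sided alpha of 5% is used to assess the alternative hypothesis that the boost arms have a FFDM rate" of 95% or better at five years, against 90%.
- **Secondary endpoints with formal power assessment.** Boost is powered for biochemical control only.
- **Non-inferiority of short fractionation.** The only toxicity limits are here: "Defining boundaries of non-inferiority at 15% for GI events and 27% of GU events".
- **Heterogeneity of treatment effect.** The split is the same. For boost, "With regards to superiority of focal boost we will test for heterogeneity for age effect of HR for FFDM", with biochemical control added. GI and GU toxicity appear under fractionation.

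Boost toxicity appears in several places. CTCAE toxicity is in the list of secondary endpoints. For acute toxicity after 400 patients, "a planned publication is made comparing all four arms with approximately 100 patients each". The organs-at-risk section and Appendix B set isotoxic dose constraints. The section on potential risks acknowledges that some extra urinary risk with boost cannot be ruled out. The section on withdrawal of consent sets intention-to-treat analysis and continued follow-up for primary and secondary endpoints.

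**The concern.** The two Purpose questions use nearly the same toxicity condition, yet only the fractionation question receives limits. Read literally, question 1 has two halves, and nothing says what boost v no-boost toxicity result would satisfy the second.

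The other toxicity provisions do not obviously fill the gap. The dose constraints govern the treatment plan rather than observed events. The acute comparison has about 100 patients per arm and no threshold. In the late dose-response analysis "the trial arm will not be disclosed to the investigators", so it cannot compare boost with no boost.

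At stake would be the claim that boost is both better and no more toxic. With no rule set beforehand, a non-significant toxicity difference might be reported as no increase, or a margin might be chosen once the data are known.

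**Working it through.** **Inputs.** The Study design section gives reference grade 2 or worse prevalence at about 1 year of 10% (GI) and 20% (GU), and a dropout hazard of 0.039 per year. The dimensioning sections give 4 × 254 = 1,016 patients, so 508 v 508 for each factor; limits of 15% and 27%, so margins of 5 and 7 points; FFDM 90% v 95% at 5 years; one-sided 5% for FFDM; and 5 years of accrual plus 1 year. No alpha is stated for the toxicity test, so 5% and 2.5% one-sided are both shown. The toxicity calculations assume that both fractionation schedules share the reference rates.

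**The plan's own figures.**

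FFDM, exponential: HR = ln 0.95 / ln 0.90 = 0.487, with about 49.8 events at 5+1 years. Power is 81.4% (Schoenfeld) or 78.5% (Freedman), against the stated 80%. At 5+5 years there are 96.7 events and power is 97.1% or 96.0%, against the stated 96%.

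Fractionation limits: power = Φ(Δ/SE − z), with SE = √(2p(1−p)/n).

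- GI: SE = √(2 × 0.10 × 0.90/508) = 0.0188. Power is 84.4% at one-sided 5% and 75.7% at 2.5%.
- GU: SE = √(2 × 0.20 × 0.80/508) = 0.0251. Power is 87.4% at 5% and 79.6% at 2.5%.

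The stated power above 80% on both endpoints is therefore reproduced as a non-inferiority test at one-sided 5%.

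**What the design delivers on boost toxicity as it stands.** The boost margin is also 508 v 508. The 95% half-width is 1.96 × SE:

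- GI: 1.96 × 0.0188 = 3.7 points.
- GU: 1.96 × 0.0251 = 4.9 points.

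With 10% of 1-year assessments missing (457 v 457), these become 1.96 × √(0.18/457) = 3.9 and 1.96 × √(0.32/457) = 5.2 points.

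**What a formal limit would add.** Suppose the fractionation margins were reused for boost, although they were not set for it. Power with no true increase, taking GI and GU as independent:

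| One-sided alpha | GI | GU | Both | Largest passing rise, GI / GU |
|---|---|---|---|---|
| 5% | 84% | 87% | 0.844 × 0.874 = 74% | 1.9 / 2.9 points |
| 2.5% | 76% | 80% | 0.757 × 0.796 = 60% | 1.3 / 2.1 points |

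A boost that truly adds no toxicity would miss at least one limit 26% to 40% of the time. If a boost claim also required FFDM superiority (stated power 80% at 5+1 years, again taken as independent), joint power would be 0.80 × 0.737 = 59% or 0.80 × 0.603 = 48%. Meeting the limits would still exclude only rises of 5 and 7 points or more, not every rise.

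**The case for a change.** The best argument for a change is that a condition written into the first trial question is an objective rather than an analysis detail, and that the Protocol itself fixed the matching limits for question 2. The announcement of a statistical analysis plan follows the heterogeneity tests, which for boost do not include toxicity. There is also a known misreading to guard against. If a non-significant two-sided 5% test were taken as no increase, a true rise from 10% to 15% GI would go undetected about 33% of the time, and a true rise from 20% to 27% GU about 25% of the time.

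Part of this stands. The Purpose sentence reaches further than the boost design, and absence of significance would be a poor basis for claiming unchanged toxicity.

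The rest does not carry. Question 2 has limits because toxicity is the confirmatory endpoint of that comparison, whereas the boost comparison has FFDM. The section on potential risks describes the boost concept as a test of tumour control with surrounding-organ dose held down, and openly allows for residual urinary risk. No section commits the trial to declaring toxicity unchanged, or to judging it by a significance test. The statement about the analysis plan says that it will be published before data analysis begins, which is the usual place for the comparison of a secondary safety endpoint. The arm-blinded dose-response study answers a different question and does not prevent an ordinary comparison by randomised arm at the end.

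**Conclusion.** No change to the plan is needed. The Purpose section uses broad wording for a question that the design sections make precise: boost is tested for superiority on FFDM, and its toxicity is a secondary endpoint to be estimated. An analyst following the Protocol would obtain a valid FFDM test and boost v no-boost risk differences with 95% intervals of about ±3.7 points (GI) and ±4.9 points (GU), and would report those intervals rather than a bare p-value.

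Formal non-inferiority for boost toxicity is a legitimate alternative, but it is a trade-off. It needs a margin justified for boost, and with the borrowed margins it would have 60% to 74% power to meet both limits when there is no true increase. No stated power, sample size or primary conclusion depends on that choice.

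These figures rest on the assumed 10% and 20% rates applying to both schedules, 508 assessed patients per side, and independence of GI and GU for the joint power.
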